2.5.5 Unscheduled visits

Unscheduled visit measurements of laboratory data, vital signs, and ECG will not be included in the by-visit summaries, but will be used for computation of baseline, the last on-treatment value, PCSAs and the shift summaries for safety or efficacy.

They will be included in the by-visit summaries if they are re-allocated to scheduled visits (see [Section 2.5.4](#))

2.5.6 Pooling of centers for statistical analyses

Center will not be included in the statistical models for efficacy analyses. However, all centers within a country will be pooled, and country will be included as a fixed effect in a parametric statistical model (eg, ANCOVA etc) for primary and secondary efficacy endpoints. Countries with fewer than 5 randomized patients will be grouped, if patients from grouped countries are still fewer than 5, they will be further grouped with the country with the lowest number of patients that is 5 or more.

2.5.7 Statistical technical issues

None.

3 INTERIM ANALYSIS

No formal interim analysis for efficacy is planned, however analysis of primary and secondary endpoints at Week 26 will be considered final at the time of first step analyses described below. The study analyses will be conducted in 2 steps:

- First step: Efficacy analyses up to Week 26, and interim safety analyses.

The first step analyses will be conducted when all patients have been randomized and have all their data, at the minimum up to Week 26 (Visit 8), collected and validated. For this analysis the common cut-off date is 10 days after the date of last patient last Week 26 visit. The first step analyses will include:

- Efficacy analyses up to Week 26, which are considered as the final analyses for primary and secondary endpoints. Analyses beyond week 26 will be descriptive,
- Safety analysis of the key secondary safety endpoint of BMD at Week 26,
- Interim safety analyses which will be performed on all safety data collected and validated at the time of the first step analyses.

The first step analyses will not be used to change the conduct of the ongoing study in any aspect. Since the primary efficacy and secondary analyses would have been concluded at the time of the first step analyses, the significance level for the study remains at 0.05 (see [Section 2.4.4.4](#)). The first step analyses will be included in the submission dossier to health authorities.

Individuals who are involved in the unblinding of the first step analysis will not be involved in the conduct of the study afterwards.

- Second step: final analyses.

The second step analyses will be conducted at the end of the study. The second step analyses will include the final analyses of efficacy endpoints at Week 52 and Week 104 and safety endpoints on the 104-week entire treatment period, which will be descriptive only.

Analyses methods and conventions described in the other sections of this SAP will be applied for all analyses as appropriate. The following additional rules will apply for the first-step analyses:

- Patients without end of treatment visit performed at the time of the cut-off date will be considered as ongoing and exposed up to the cut-off date. Therefore:
- Any assessments within analysis windows up to Week 26 will be taken into account (may include few unscheduled data after the cut-off date),
- Patients who did not complete 104-week entire treatment period nor prematurely discontinued the study treatment at cut-off date will be analyzed as “ongoing” in the disposition summary,
- Their TEAE period, and on-study observation period will end at the cut-off date,

- Their treatment duration will be derived by considering date of cut-off as last administration date,
- Analyses of percentage of days with under/above-planned dosing and compliance will be performed up to last administration reported in the e-CRF before the last visit taking into consideration of the cut-off date,
- AEs occurring, worsening or becoming serious after the cut-off date will not be included in the analyses. However, any available outcome before database lock, regardless of timing in relation to the cut-off date, of an adverse event starting prior to the cut-off date will be taken into account. Medications, treatment discontinuations/completions, and deaths occurring after the cut-off date will not be included in the analyses,
- For time to severe or documented symptomatic hypoglycemia at the 1st step analysis, the censoring date is min (EOT+1, EOS, common cut-off date),
- Post-treatment epoch, post-study period are not applicable for ongoing patients. Analyses of post-treatment AEs, post-study deaths, and post-treatment medications will be performed for patients who either completed or prematurely discontinued the treatment before or at the cut-off date,
- Status at last study contact will be provided for patients who either completed or prematurely discontinued the study before or at the cut-off date.

An independent DMC will monitor and assess the safety of patients from this trial through periodic review of the accumulated safety data provided by an independent statistical group. Related details are provided in separate documents (DMC charter and DMC SAP).

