### **10.1.3 Double-blind, Randomized Extension Period (Week 27 to Week 104)**

#### **10.1.3.1 On-site visits from Visit 9 to Visit 12 (Week 27 to Week 86)**

The following procedures will be performed at each Visit, except as specified:

- Concomitant medications will be assessed.
- Measurement of BW.
- Measurement of height only at Visit 10 (Week 52).
- Abbreviated physical examination and vital signs (see [Appendix C](#)).
- IMP accountability and compliance with double-blind IMP treatment.
- IRT will be notified for IMP resupply.

- AEs/SAEs/AESI/EOSI and hypoglycemia (if any) occurring since the previous visit will be reported.
- Diet and exercise instruction will be provided, except at Visit 9 (Week 39).
- Patient diary will be collected and reviewed and a new one will be dispensed. Instructions/training will be provided as needed.
- SMBG records will be reviewed.
- Patients will be evaluated for glycemc rescue.
- Instructions on glucose testing, basic GU hygiene, hydration, and recognizing DKA symptoms will be provided.
- Central laboratory testing:
  - FPG: Visit 10 (Week 52) and Visit 12 (Week 86).
  - HbA1c: Visit 10 (Week 52) and Visit 12 (Week 86).
  - Clinical chemistry, including amylase and lipase: Visit 10 (Week 52) and Visit 12 (Week 86).
  - Hematology: Visit 10 (Week 52) and Visit 12 (Week 86).
  - Serum estradiol (only for women): Visit 10 (Week 52).
  - Bone turnover markers: Visit 10 (Week 52).
  - Markers of calcium metabolism: Visit 10 (Week 52).
  - Urinalysis (dipstick and microscopy): Visit 10 (Week 52) and Visit 12 (Week 86).
  - Albumin, creatinine, calcium, phosphorus, and magnesium concentration in 24-hour urine will be done at Visit 10 (Week 52).
- Double-blind IMP is dispensed.
- At Visit 10 (Week 52) confirm with the central review facility that the DXA procedures for Visit 8 were performed successfully. In case the DXA scan needs to be repeated, or has not been done yet, instruct the patients to perform the DXA scan within the next 7 days.
- Patients are instructed to return to the site in the fasting state for the next visit, except for Visit 9 (Week 39) and Visit 11 (Week 68) when fasting is not required.
- For accountability and compliance purposes, patients are instructed to return to the site at the next visit bringing their used, partially used, or not used medication kit(s).

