2.4.5.2 Analyses of hypoglycemia

Analyses of hypoglycemia will be performed on the TEAE period as defined in [Section 2.1.4](#). Hypoglycemia will be classified as severe hypoglycemia, documented symptomatic hypoglycemia, asymptomatic hypoglycemia, probable symptomatic hypoglycemia or relative hypoglycemia (See [Section 2.1.4.1](#)).

The number (%) of patients with 1) any hypoglycemia, 2) severe hypoglycemia and documented symptomatic hypoglycemia will be summarized respectively by treatment group during the TEAE period, as well as the incidence rate in patient years. Two types of incidence rates will be presented: the number of patients with event(s) per 100 patient-years (calculated as the number of patients with at least 1 event/ total exposure in 100 patient-years) and the total number of events per 100 patient-years (calculated as the total number of events / total exposure in 100 patient-years). Note: Note: here exposure in days is duration of treatment-emergent AE period, ie, duration of IMP treatment in days +1 ([Section 2.1.4](#)).

The summary of frequency and incidence rate in patient-years for severe hypoglycemia or documented symptomatic hypoglycemia will be provided as appropriate by gender, age group (≥ 55 to < 65 , ≥ 65 years), race (White, Black or African American, Asian, Other).

A KM curve will be provided by treatment group for the time to first severe hypoglycemia or documented symptomatic hypoglycemia during the TEAE period for the 104-week entire treatment period only (see [Section 2.4.5](#)).

Documented symptomatic hypoglycemia may be presented by ≤ 70 mg/dL (3.9 mmol/L) and < 54 mg/dL (3.0 mmol/L) respectively, as appropriate.

A listing of patients for all events reported on the dedicated e-CRF “Hypoglycemic event information” page will be provided with each category flagged (ie, severe hypoglycemia, documented symptomatic hypoglycemia, asymptomatic hypoglycemia, probable symptomatic hypoglycemia and relative hypoglycemia).

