4 DATABASE LOCK

Two database locks will be done:

- First database lock (for first step analysis): will include all available data on all randomized patients up to the common cut-off date as defined in [Section 3](#). This database lock is planned to be done approximately 4 weeks after the common cut-off date.
- Final database lock (for second step analysis): will include all data, including follow-up, for all randomized patients. This database lock is planned to be done approximately 4 weeks after last patient last visit.

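### First-step hypoglycemia rates for patients still on treatment divide by exposure up to the cut-off, while routine collection of episodes stops at the last visit, so the absolute rates are probably too low.

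*SAP*

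**What the plan says.** **Cut-off.** SAP section 3: "For this analysis the common cut-off date is 10 days after the date of last patient last Week 26 visit".

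**Denominator.** For ongoing patients the same section sets the end of follow-up at that date: "Their TEAE period, and on-study observation period will end at the cut-off date". Treatment duration follows: "Their treatment duration will be derived by considering date of cut-off as last administration date". SAP 2.4.5.2 defines two rates per 100 patient-years, one counting patients with at least one event and one counting all events. The second is "calculated as the total number of events / total exposure in 100 patient-years". For both, "here exposure in days is duration of treatment-emergent AE period, ie, duration of IMP treatment in days +1".

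**Numerator.** Protocol 9.2.1.8 and 10.6.1 have patients record episodes in a diary that is collected and reviewed at visits. At extension visits, Protocol 10.1.3.1 says: "AEs/SAEs/AESI/EOSI and hypoglycemia (if any) occurring since the previous visit will be reported". The flow chart places these visits at Days 182, 273, 364, 476, 602 and 728. No contact is scheduled at the cut-off.

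**Lock.** SAP section 4: "This database lock is planned to be done approximately 4 weeks after the common cut-off date".

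**Compliance.** In the same list of first-step rules, dosing analyses stop earlier: "compliance will be performed up to last administration reported in the e-CRF before the last visit".

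**Time to first event.** SAP section 3 censors first-step hypoglycemia at the earliest of EOT+1, EOS and the common cut-off. The censoring table in SAP 2.5.4 has the Week 26 visit date in place of the cut-off, with a pointer to section 3.

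**The concern.** A rate per patient-year needs events and time at risk to cover the same period. Here the time at risk for an ongoing patient runs to the cut-off. A non-serious episode after that patient's last visit is normally still in the diary at home. The time counts in the denominator, but the episode is missing from the numerator unless a visit or contact brings it in before the lock.

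The SAP applies this logic to compliance but not to hypoglycemia, which is expressed per patient-year and so needs it. The first-step results go into the submission dossier, where the absolute entire-period hypoglycemia rates would look lower than they are.

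**Working it through.** The documents state no hypoglycemia rate, gap or bias, so there is no figure of theirs to reproduce. The check estimates how much of the denominator was not covered by routine collection.

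**Inputs from the documents.** Visit days as above. Shortest time on study for an ongoing patient at the cut-off: 182 + 10 = 192 days. Time from cut-off to lock: about 28 days.

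**Assumptions (not in the documents).** Accrual is uniform over A days, so time on study at the cut-off runs evenly from 192 to 192 + A. The event rate is constant. Nothing is captured between visits. The extra day in the exposure definition is ignored.

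**Formula for the total-event rate.** Understatement = mean(cut-off day − last visit day) / mean(exposure to cut-off). A patient's gap is set to zero if the next visit falls within the recovery time allowed after the cut-off: 0, 14 or 28 days.

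**Single patients.** The last patient in has 10 of 192 days uncovered: 10/192 = 5.2%. A patient at Day 244 has 244 − 182 = 62 days uncovered: 62/244 = 25%. That patient's next visit, Day 273, comes 29 days after the cut-off and so just misses the lock.

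**Averages.**
- A = 0: 10/192 = 5.2%.
- A = 80: mean gap 10 + 40 = 50, mean exposure 192 + 40 = 232, and 50/232 = 21.6%.
- A = 90: for the first 81 days the gap runs from 10 to 91 (mean 50.5). For the last 9 days it restarts at Visit 9 (mean 4.5). Mean gap = (81 × 50.5 + 9 × 4.5)/90 = 45.9, and 45.9/237 = 19.4%.

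| Accrual | No recovery | 14 days | 28 days (all visits before lock) |
|---|---|---|---|
| 0 days | 5.2% | 5.2% | 5.2% |
| 80 days | 21.6% | 15.7% | 10.4% |
| 90 days | 19.4% | 13.9% | 9.3% |
| 180 days | 16.3% | 11.6% | 7.8% |
| 270 days | 14.8% | 12.1% | 8.4% |
| 365 days | 13.0% | 10.2% | 7.8% |
| 63 weeks | 12.6% | 9.6% | 7.0% |
| 480 days | 12.0% | 9.4% | 7.1% |

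The value near 22% is a narrow peak: it occurs when accrual ends just before the first patients reach Visit 9. If 20% of patients had stopped early (assumed mean exposure 91 days, fully collected), the uniform-accrual figures would fall by at most about 2 points. Front-loaded or back-loaded accrual over 90 to 480 days gives 6.2% to 20.9%.

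**Which accrual length is plausible.** SAP 1.5 dates the first enrollment to 14 March 2018. SAP version 3 was issued on 30 January 2020, 687 days later, and still describes the first step as to come. If it preceded the first lock, the cut-off was at least 687 − 28 = 659 days after first enrollment. Subtracting 28 days of screening and run-in, 182 days to Week 26 and the 10 days leaves 439 days, or about 63 weeks of accrual. The table then gives 7.0% to 12.6%.

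**Patients-with-event rate.** Uncovered time after a patient's first event costs this numerator nothing. At an assumed 1 event per patient-year and 52 weeks of accrual, the understatement is 8.4%, 6.5% and 4.8% for the three recovery times, against 13.0%, 10.2% and 7.8% for total events. At 0.2 per year the two rates are close.

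**Where the gap is zero.** Under SAP 2.5.4 the core TEAE period of continuing patients ends at Visit 8, so events and exposure stop together.

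**The case against.** The SAP does not cut events at the last visit. The first lock takes all available data up to the cut-off, and a visit in the following 4 weeks can supply earlier episodes. Protocol flow chart note f mentions discussing glucose results by telephone, and section 10.1 allows extra contacts. Episodes with unconsciousness, coma or seizure are also SAEs, entered within 24 hours. All of this stands. It reduces the shortfall by an amount the documents do not let us estimate. It does not remove it, because no contact is required at the cut-off and most ongoing patients will have no scheduled visit in the 4 weeks before the lock.

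A single cut-off for exposure and treatment-emergent events is also a consistent convention, and the safety analysis is descriptive. That is fair for percentages of patients. It does not help a rate whose denominator includes time that was not observed, and the SAP already departs from the convention for compliance.

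A reader might go on to infer that the time-to-first-event curve certainly counts unobserved time as event-free. The documents do not settle this: the SAP 2.5.4 table censors at the Week 26 visit, which leaves no such tail, while section 3 censors at the cut-off.

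**Conclusion.** The mismatch is real and its likely direction is downward, but it is confined to the absolute entire-period hypoglycemia rates at the first step. For total events the understatement is about 5% to 19%, touching 22% around 80 days of accrual. It is about 7% to 13% if accrual was about 63 weeks, which itself assumes that SAP version 3 preceded the first lock. These figures rest on uniform accrual, a constant event rate and no capture between visits. Any such capture lowers them, and the patients-with-event rate is affected less.

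Two stronger readings are not supported. One is a fixed percentage for all reported rates: accrual length is not stated, and the two rates behave differently. The other is a distorted treatment comparison: the visit schedule and cut-off are the same in all arms, so ratios should be largely preserved. The 26-week core rate and the second-step analysis are not affected. This is a minor point, worth correcting because the correction is cheap.

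**What to change.** In SAP section 3, add that for patients ongoing at the first step, hypoglycemia exposure, event counting and censoring, for both rates and the time-to-event curve, end at the last visit or contact on or before the cut-off at which hypoglycemia was reviewed. This follows the rule already written for compliance.

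State as well that any episode reported after that date and up to the cut-off, for example as an SAE, stays in the n (%) table and the listing, so that no known event is lost. A footnote should explain why such an episode is not in the rate.

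Make the first-step hypoglycemia censoring date in the SAP 2.5.4 table and the one in section 3 agree.

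The cost is a short SAP addition, one table entry and a different end date in the first-step hypoglycemia programs. Some exposure per ongoing patient drops out of this interim rate: 46 to 52 days on average in the model for accrual of 90 to 480 days. Hypoglycemia would also have a different exposure end date from the other safety tables. Trial conduct and the final analysis do not change.

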4 DATABASE LOCK

Two database locks will be done:

- First database lock (for first step analysis): will include all available data on all randomized patients up to the common cut-off date as defined in [Section 3](#). This database lock is planned to be done approximately 4 weeks after the common cut-off date.
- Final database lock (for second step analysis): will include all data, including follow-up, for all randomized patients. This database lock is planned to be done approximately 4 weeks after last patient last visit.

5 SOFTWARE DOCUMENTATION

All summaries and statistical analyses will be generated using SAS® Version 9.2 or higher.

7 LIST OF APPENDICES

Appendix A: Potentially clinically significant abnormalities (PCSA) criteria

Appendix B: List of PTs for select EOSIs (MedDRA v22.0)

Appendix C: Summary of statistical analyses

Appendix D: Study Flow Chart

Appendix A Potentially clinically significant abnormalities criteria

CRITERIA for POTENTIALLY CLINICALLY SIGNIFICANT ABNORMALITIES for phase 2/3 studies (oncology excepted) (From BTD-009536 May 21, 2014)

Parameter	PCSA	Comments
Clinical Chemistry		
ALT	By distribution analysis :	Enzymes activities must be expressed in ULN, not in IU/L.
	>3 ULN	
	>5 ULN	Concept paper on DILI – FDA draft Guidance Oct 2007.
	>10 ULN	Internal DILI WG Oct 2008.
	>20 ULN	Categories are cumulative. First row is mandatory. Rows following one mentioning zero can be deleted.
AST	By distribution analysis :	Enzymes activities must be expressed in ULN, not in IU/L.
	>3 ULN	
	>5 ULN	Concept paper on DILI – FDA draft Guidance Oct 2007.
	>10 ULN	Internal DILI WG Oct 2008.
	>20 ULN	Categories are cumulative. First row is mandatory. Rows following one mentioning zero can be deleted.
Alkaline Phosphatase	>1.5 ULN	Enzymes activities must be expressed in ULN, not in IU/L. Concept paper on DILI – FDA draft Guidance Oct 2007. Internal DILI WG Oct 2008.
Total Bilirubin	>1.5 ULN	Must be expressed in ULN, not in $\mu\text{mol/L}$ or mg/L . Categories are cumulative.
	>2 ULN	Concept paper on DILI – FDA draft Guidance Oct 2007. Internal DILI WG Oct 2008.
Conjugated Bilirubin >35% Total Bilirubin and TBILI>1.5 ULN		Conjugated bilirubin dosed on a case-by-case basis.

CRITERIA for POTENTIALLY CLINICALLY SIGNIFICANT ABNORMALITIES**for phase 2/3 studies (oncology excepted)****(From BTD-009536 May 21, 2014)**

Parameter	PCSA	Comments
ALT and Total Bilirubin	ALT>3 ULN and TBILI>2 ULN	Concept paper on DILI – FDA draft Guidance Oct 2007. Internal DILI WG Oct 2008. To be counted within a same treatment phase, whatever the interval between measurement.
CPK	>3 ULN >10 ULN	FDA Feb 2005. Am J Cardiol April 2006. Categories are cumulative. First row is mandatory. Rows following one mentioning zero can be deleted.
CLcr (mL/min) (Estimated creatinine clearance based on the Cockcroft-Gault equation)	<15 (end stage renal disease) ≥15 - <30 (severe decrease in GFR) ≥30 - <60 (moderate decrease in GFR) ≥60 - <90 (mild decrease in GFR) ≥90 (normal GFR)	FDA draft Guidance 2010 Pharmacokinetics in patients with impaired renal function-study design, data analysis, and impact on dosing and labeling
eGFR (mL/min/1.73m ²) (Estimate of GFR based on an MDRD equation)	<15 (end stage renal disease) ≥15 - <30 (severe decrease in GFR) ≥30 - <60 (moderate decrease in GFR) ≥60 - <90 (mild decrease in GFR) ≥90 (normal GFR)	FDA draft Guidance 2010 Pharmacokinetics in patients with impaired renal function-study design, data analysis, and impact on dosing and labeling
Creatinine	≥150 μmol/L (Adults) ≥30% change from Baseline ≥100% change from Baseline	Benichou C., 1994.
Uric Acid		Harrison- Principles of internal Medicine 17 th Ed., 2008.
Hyperuricemia	>408 μmol/L	
Hypouricemia	<120 μmol/L	
Blood Urea Nitrogen	≥17 mmol/L	
Chloride	<80 mmol/L >115 mmol/L	
Sodium	≤129 mmol/L ≥160 mmol/L	

CRITERIA for POTENTIALLY CLINICALLY SIGNIFICANT ABNORMALITIES
for phase 2/3 studies (oncology excepted)
(From BTD-009536 May 21, 2014)

Parameter	PCSA	Comments
Potassium	<3 mmol/L ≥5.5 mmol/L	FDA Feb 2005.
Total Cholesterol	≥7.74 mmol/L	Threshold for therapeutic intervention.
Triglycerides	≥4.6 mmol/L	Threshold for therapeutic intervention.
Lipasemia	≥3 ULN	
Amylasemia	≥3 ULN	
Glucose		
Hypoglycaemia	≤3.9 mmol/L and <LLN	ADA May 2005.
Hyperglycaemia	≥11.1 mmol/L (unfasted); ≥7 mmol/L (fasted)	ADA Jan 2008.
HbA1c	>8%	
Albumin	≤25 g/L	
CRP	>2 ULN or >10 mg/L (if ULN not provided)	FDA Sept 2005.
Hematology		
WBC	<3.0 Giga/L (Non-Black); <2.0 Giga/L (Black) ≥16.0 Giga/L	Increase in WBC: not relevant. To be interpreted only if no differential count available.
Lymphocytes	>4.0 Giga/L	
Neutrophils	<1.5 Giga/L (Non-Black); <1.0 Giga/L (Black)	International Consensus meeting on drug-induced blood cytopenias, 1991. FDA criteria.
Monocytes	>0.7 Giga/L	
Basophils	>0.1 Giga/L	
Eosinophils	>0.5 Giga/L or >ULN (if ULN ≥0.5 Giga/L)	Harrison- Principles of internal Medicine 17 th Ed., 2008.
Hemoglobin	≤115 g/L (Male); ≤95 g/L (Female) ≥185 g/L (Male); ≥165 g/L (Female) Decrease from Baseline ≥20 g/L	Criteria based upon decrease from Baseline are more relevant than based on absolute value. Other categories for decrease from Baseline can be used (≥30 g/L, ≥40 g/L, ≥50 g/L).
Hematocrit	≤0.37 v/v (Male) ; ≤0.32 v/v (Female) ≥0.55 v/v (Male) ; ≥0.5 v/v (Female)	

CRITERIA for POTENTIALLY CLINICALLY SIGNIFICANT ABNORMALITIES

for phase 2/3 studies (oncology excepted)

(From BTD-009536 May 21, 2014)

Parameter	PCSA	Comments
RBC	≥6 Tera/L	Unless specifically required for particular drug development, the analysis is redundant with that of Hb. Otherwise, consider FDA criteria.
Platelets	<100 Giga/L ≥700 Giga/L	International Consensus meeting on drug-induced blood cytopenias, 1991.
Urinalysis		
pH	≤4.6 ≥8	
Vital signs		
HR	≤50 bpm and decrease from Baseline ≥20 bpm ≥120 bpm and increase from Baseline ≥20 bpm	To be applied for all positions (including missing) except STANDING.
SBP	≤95 mmHg and decrease from Baseline ≥20mmHg ≥160 mmHg and increase from Baseline ≥20 mmHg	To be applied for all positions (including missing) except STANDING.
DBP	≤45 mmHg and decrease from Baseline ≥10 mmHg ≥110 mmHg and increase from Baseline ≥10 mmHg	To be applied for all positions (including missing) except STANDING.
Orthostatic Hypotension		
Orthostatic SDB	≤-20 mmHg	
Orthostatic DBP	≤-10 mmHg	
Weight	≥5% increase from Baseline ≥5% decrease from Baseline	FDA Feb 2007.

CRITERIA for POTENTIALLY CLINICALLY SIGNIFICANT ABNORMALITIES

for phase 2/3 studies (oncology excepted)

(From BTD-009536 May 21, 2014)

Parameter	PCSA	Comments
ECG		Ref.: ICH E14 guidance (2005) and E14 Q&A (2012), and Cardiac Safety Research Consortium White Paper on PR and QRS (Nada et al. Am Heart J. 2013; 165(4) : 489-500)
HR	<50 bpm	Categories are cumulative
	<50 bpm and decrease from Baseline \geq 20 bpm	
	<40 bpm	
	<40 bpm and decrease from Baseline \geq 20 bpm	
	<30 bpm	
	<30 bpm and decrease from Baseline \geq 20 bpm	
	>90 bpm	Categories are cumulative
	>90 bpm and increase from Baseline \geq 20bpm	
	>100 bpm	
	>100 bpm and increase from Baseline \geq 20bpm	
	>120 bpm	
	>120 bpm and increase from Baseline \geq 20 bpm	
PR	>200 ms	Categories are cumulative
	>200 ms and increase from Baseline \geq 25%	
	> 220 ms	
	>220 ms and increase from Baseline \geq 25%	
	> 240 ms	
	> 240 ms and increase from Baseline \geq 25%	
QRS	>110 ms	Categories are cumulative
	>110 msec and increase from Baseline \geq 25%	
	>120 ms	
	>120 ms and increase from Baseline \geq 25%	

CRITERIA for POTENTIALLY CLINICALLY SIGNIFICANT ABNORMALITIES

for phase 2/3 studies (oncology excepted)

(From BTD-009536 May 21, 2014)

Parameter	PCSA	Comments
QT	>500 ms	
QTc	Absolute values (ms)	To be applied to any kind of QT correction formula. Absolute values categories are cumulative
	>450 ms	
	>480 ms	QTc >480 ms and Δ QTc >60 ms are the 2 PCSA
	>500 ms	categories to be identified in individual subjects/patients listings.
	Increase from Baseline	
	Increase from Baseline]30-60] ms	
	Increase from Baseline >60 ms	

